6.2 Randomization

A participant's randomization assignment will be computer generated and provided to the HVTN CRS pharmacist through a web-based randomization system. At each institution, the pharmacist with primary responsibility for dispensing study products is charged with maintaining security of the treatment assignments (except in emergency situations as specified in the HVTN Manual of Operations [MOP]).

6.3 Blinding

Participants and site staff (except for site pharmacists) will be blinded as to participant treatment arm assignments (eg, vaccine or control). Study product assignments are accessible to those HVTN CRS pharmacists, DAIDS protocol pharmacists and contract monitors, and SDMC staff who are required to know

this information in order to ensure proper trial conduct. Any discussion of study product assignment between pharmacy staff and any other HVTN CRS staff is prohibited. The HVTN SMB members also are unblinded to treatment assignment in order to conduct review of trial safety.

When a participant leaves the trial prior to study completion, the participant will be told he or she must wait until all participants are unblinded to learn his or her treatment assignment.

In some cases, the CRS, PSRT, or study sponsor may believe unblinding of the site Principal Investigator (PI) and participant would be appropriate to facilitate the clinical management of an AE or SAE. The HVTN Unblinding MOP specifies procedures for emergency unblinding, and for early unblinding for medical reasons.

6.4 Statistical analyses

This section describes the final study analyses, unblinded as to treatment arm assignment. All data from enrolled participants will be analyzed according to the initial randomization assignment regardless of how many vaccinations they received. In the rare instance that a participant receives the wrong treatment at a specific vaccination time, the Statistical Analysis Plan (SAP) will address how to analyze the participant's safety data. Analyses are modified intent-to-treat in that individuals who are randomized but not enrolled do not contribute data and hence are excluded. Because of blinding and the brief length of time between randomization and enrollment—typically no more than 4 working days—very few such individuals are expected.

Analyses for primary endpoints will be performed using SAS and R. All other descriptive and inferential statistical analyses will be performed using SAS, StatXact, or R statistical software.

No formal multiple comparison adjustments will be employed for multiple safety endpoints, multiple primary immunogenicity endpoints, or secondary endpoints. However, multiplicity adjustments will be made for certain immunogenicity assays, as discussed below, when the assay endpoint is viewed as a collection of hypotheses (eg, testing multiple peptide pools to determine a positive response).

6.4.1 Analysis variables

The analysis variables consist of baseline participant characteristics, safety, and immunogenicity for primary- and secondary-objective analyses.

6.4.2 Baseline comparability

Treatment arms will be compared for baseline participant characteristics using descriptive statistics.

6.4.3 Safety/tolerability analysis

Since enrollment is concurrent with receiving the first vaccination, all participants will have received at least 1 vaccination and therefore will provide some safety data.

6.4.3.1 Reactogenicity

The number and percentage of participants experiencing each type of reactogenicity sign or symptom will be tabulated by severity and treatment arm and the percentages displayed graphically by arm. For a given sign or symptom, each participant's reactogenicity will be counted once under the maximum severity for all injection visits. In addition to the individual types of events, the maximum severity of local pain or tenderness, induration or erythema, and systemic symptoms will be calculated. Wilcoxon rank sum tests will be used to test for differences in severity between arms.

6.4.3.2 AEs and SAEs

AEs will be summarized using Medical Dictionary for Regulatory Activities (MedDRA) System Organ Class and preferred terms. Tables will show by treatment arm the number and percentage of participants experiencing an AE within a System Organ Class or within preferred term category by severity or by relationship to study product. For the calculations in these tables, a participant with multiple AEs within a category will be counted once under the maximum severity or the strongest recorded causal relationship to study product. Formal statistical testing comparing arms is not planned since interpretation of differences must rely heavily upon clinical judgment.

A listing of SAEs reported to the DAIDS Regulatory Support Center (RSC) Safety Office will provide details of the events including severity, relationship to study product, time between onset and last vaccination, and number of vaccinations received.

6.4.3.3 Local laboratory values

Box plots of local laboratory values will be generated for baseline values and for values measured during the course of the study by treatment arm and visit. Each box plot will show the first quartile, the median, and the third quartile. Outliers (values outside the box plot) will also be plotted. If appropriate, horizontal lines representing boundaries for abnormal values will be plotted.

For each local laboratory measure, summary statistics will be presented by treatment arm and timepoint, as well as changes from baseline for postenrollment values. In addition, the number (percentage) of participants with local laboratory values recorded as meeting Grade 1 AE criteria or above as specified in the Division of AIDS Table for Grading the Severity of Adult and Pediatric Adverse Events (see Section 11.2.2) will be tabulated by treatment arm for each postvaccination timepoint. Reportable clinical laboratory abnormalities without an

associated clinical diagnosis will also be included in the tabulation of AEs described above.

6.4.3.4 Dose Escalation

All available safety data through 2 weeks after the first vaccination for Group 1 participants will be evaluated by the PSRT to inform whether to proceed with escalation to the higher dose (Group 2).

6.4.3.5 Reasons for vaccination discontinuation and early study termination

The number and percentage of participants who discontinue vaccination and who terminate the study early will be tabulated by reason and treatment arm.

6.4.4 Immunogenicity analysis

6.4.4.1 General approach

For the statistical analysis of immunogenicity endpoints, data from enrolled participants will be used according to the initial randomization assignment regardless of how many injections they received. Additional analyses may be performed, limited to participants who received all scheduled injections per protocol. Assay results that are unreliable, from specimens collected outside of the visit window, or from HIV-infected participants postinfection are excluded. Since the exact date of HIV infection is unknown, any assay data from blood draws 4 weeks prior to an infected participant's last seronegative sample and thereafter may be excluded. If an HIV-infected participant does not have a seronegative sample postenrollment, then all data from that participant may be excluded from the analysis.

Discrete categorical assay endpoints (eg, response rates) will be analyzed by tabulating the frequency of positive response for each assay by antigen and treatment arm at each timepoint for which an assessment is performed. Crude response rates will be presented with their corresponding 95% confidence interval estimates calculated using the score test method (33). Because of the small numbers of control participants in each group, no adjustment will be made to the vaccine arm estimates for the false positive rates in the control arms. Barnard or Fisher's exact tests, as specified in the SAP, will be used to compare the response rates of any 2 vaccine arms, with a significant difference declared if the 2-sided p-value is ≤ 0.05 . In general Barnard's is preferred since under most circumstances it is more powerful than Fisher's (34).

In addition to response rate estimates for each timepoint, the probability of observing at least 1 positive response by a given timepoint and the probability of observing more than 1 positive response by a given timepoint will be estimated, with corresponding confidence intervals, for each vaccine arm using maximum likelihood-based methods (35).

For quantitative assay data (eg, binding antibody multiplex assay [BAMA]), graphical and tabular summaries of the distributions by antigen, treatment arm, and timepoint will be made. For all primary and secondary immunogenicity endpoints, box plots and plots of estimated reverse cumulative distribution curves will be used for graphical display of all of the study arms. Typically, the results will be shown for each vaccine arm and for the set of control arms pooled into one group.

Based upon previous HVTN trials, missing 10% of immunogenicity results for a specific assay is common due to study participants terminating from the study early, problems in shipping specimens, or low cell viability of processed PBMCs. To achieve unbiased statistical estimation and inferences with standard methods applied in a complete-case manner (only including participants with observed data in the analysis), missing data need to be missing completely at random (MCAR). Following the most commonly used definition, MCAR assumes that the probability of an observation being missing does not depend on any participant characteristics (observed or unobserved data [ie, the observed data are just a random sample of all the potential data]). When missing data are minimal (specifically if no more than 20% of participants are missing any values), then standard complete-case methods will be used, because violations of the MCAR assumption will have little impact on the estimates and hypothesis tests.

If a substantial amount of immunogenicity data are missing for an endpoint (at least 1 value missing from more than 20% of participants), then using the methods that require the MCAR assumption may give misleading results. In this situation, analyses of the immunogenicity endpoints at a specific timepoint will be performed with methods such as targeted minimum loss-based estimation (TMLE), using parametric generalized linear models fit by maximum likelihood based on appropriate modeling assumptions for the endpoint and adjusted using covariate adjustment, weighting methods or combined with imputation of missing data. These methods provide unbiased estimation and inferences under the parametric modeling assumptions and the assumption that the missing data are missing at random (MAR). MAR assumes that the probability of an observation being missing only depends upon the observed responses and upon observed covariates, but not upon any unobserved factors. Thus, this assumption is less stringent than the MCAR assumption. Generalized linear models for response rates will use a binomial error distribution and for quantitative endpoints, a normal error distribution. For assessing repeated immunogenicity measurement, linear mixed effects models will be used. If the immunological outcomes are left- and/or right- censored, then the linear mixed effects models of Hughes (36) will be used, because they accommodate the censoring. In addition, secondary analyses of repeated immunogenicity measurements may be done using weighted generalized estimating equation (GEE) (37) methods, which are valid under MAR. All of the models described above in this paragraph will include as covariates all available baseline predictors of the missing outcomes.

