6.1 Accrual and sample size calculations

Recruitment will target enrolling 24 healthy, HIV-uninfected adult participants aged 18 to 50 years old at low risk of HIV infection in regions where clade B is the predominant clade.

Enrollment will be concurrent with receiving the first study vaccination, thus all participants will provide some safety data. For immunogenicity analyses, however, it is possible that data may be missing for various reasons such as participants terminating from the study early, problems in shipping specimens, or low cell viability of processed peripheral blood mononuclear cells (PBMCs). Immunogenicity data from 11 phase 1 and 1 phase 2a HVTN trials, which began enrolling after June 2005 (data as of June 2011), indicate that 10% is a reasonable estimate for the rate of missing data. For this reason, the sample size calculations in Section 6.1.2 account for 10% of enrolled participants having missing data for the primary immunogenicity endpoint.

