6.1.2 Sample size calculations for immunogenicity

The main goals of this trial regarding immunogenicity outcomes involve a preliminary estimation of rates of “response” (defined as binding response positivity to the 2F5 epitope) based on data from immune assays among vaccinees. To address binding antibody endpoints, the analysis will descriptively summarize binding response positivity call rates, and for the comparison of Group 1 vs 2, test superiority of the rate of responses targeting the 2F5 binding site by Barnard’s exact test. No adjustment for multiple comparisons will be made for the use of multiple assays. The precision with which the true response rate can be estimated from the observed data depends on the true underlying response rate

and the sample size. Two-sided 95% confidence intervals for the response rate based on observing a particular rate of responses in the vaccinees is shown in [Table 6-3](#). Calculations are done using the score test method (33). The $n = 4$, $n = 13$, and $n = 18$ (for the two arms combined) assume a 10% rate of missing immunogenicity data.

Table 6-3 Two-sided 95% confidence intervals for the true response rate based on observing a particular rate of responses in the vaccinees ($n = 4$, $n = 13$, and $n = 18$)

No. of responses	Observed response rate (%)	95% Confidence interval
1/4	25	[4.6, 69.9]
2/4	50	[15, 85]
3/4	75	[30.1, 95.4]
1/13	7.7	[1.4, 33.3]
3/13	23.1	[8.2, 50.3]
5/13	38.5	[17.7, 64.5]
7/13	53.8	[29.1, 76.8]
9/13	69.2	[42.4, 87.3]
3/18	17	[5.8, 39.2]
6/18	33	[16.3, 56.3]
9/18	50	[29, 71]
12/18	67	[43.7, 83.7]
15/18	83	[60.8, 94.2]

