An alternative approach is to consider the probability of observing 0, 1 or more, and 50% or more responses for groups of sizes 4, 13 and 18; presented in [Table 6-4](#) for a range of possible true response rates. If the true rate is 20%, then there is a 59% chance of observing any responses in the Group 1 vaccine arm, a 94.5% chance of observing any responses in the Group 2 vaccine arm and a 98% chance of observing at least one response across the two arms. In all cases, the probability of observing 50% or more positive responses is in excess of 80% if the true positivity rate is at least 60%, but when the true rate is below 40%, there is at least a 50% chance of observing fewer than half respond. If the true rate is 50%, then there is a 59% chance of observing at least half (2) respond in the $n = 4$ Group 1 vaccine arm, a 71% chance of observing at least half (6, rounding down) respond in the $n = 13$ Group 2 vaccine arm and a 59% chance of observing at least half (9) respond across the two arms combined ($n = 18$).

Table 6-4 Probability of observing 0 events, 1 or more events, and 50% or more events, among groups of size 4, 13 and 18, for different true event rates

True rate (%)	Pr(0/4)	Pr(1+/4)	Pr(2+/4)	Pr(0/13)	Pr(1+/13)	Pr(6+/13)	Pr(0/18)	Pr(1+/18)	Pr(9+/18)
10	65.6	34.4	5.2	25.4	74.6	0.1	15	85	0
20	41	59	18.1	5.5	94.5	3	1.8	98.2	0.4
30	24	76	34.8	1	99	16.5	0.2	99.8	6
40	13	87	52.5	0.1	99.9	42.6	0	100	26.3
50	6.2	93.8	68.8	0	100	70.9	0	100	59.3
60	2.6	97.4	82.1	0	100	90.2	0	100	86.5
70	0.8	99.2	91.6	0	100	98.2	0	100	97.9
80	0.2	99.8	97.3	0	100	99.9	0	100	99.9
90	0	100	99.6	0	100	100	0	100	100

As shown in [Table 6-5](#), there is limited power for a formal comparison of immunogenicity response rates between vaccine arms of size $n = 13$ vs $n = 4$. For either 80% or 90% power, the sizes of differences that the trial is powered to detect are fairly large. These calculations use a Fisher's exact 2-sided test with a Type I error rate of 0.05.

Table 6-5 Power for comparison of response rates between 2 arms ($n_1 = 13$, $n_2 = 4$)

True response rate Arm 1 (%)	Minimum true response rate in Arm 2 in order to detect a difference	
	80% power	90% power
0	89	97
1	90	97
2	91	98
3	92	99
4	92	99
5	93	100

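### Barnard's test is planned for Group 1 vs Group 2, yet the detectable differences are stated for Fisher's and 6.4.4.1 allows either; at 13 vs 4 the two disagree in 4 of 70 tables

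*Combined protocol and SAP*

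**What the plan says.** Three places in the combined protocol and SAP bear on this one comparison.

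- Section 6.1.2, opening paragraph: for Group 1 vs Group 2 the analysis will "test superiority of the rate of responses targeting the 2F5 binding site by Barnard’s exact test".
- Section 6.1.2, text introducing Table 6-5 (arms of 13 and 4): "These calculations use a Fisher's exact 2-sided test with a Type I error rate of 0.05".
- Section 6.4.4.1: "Barnard or Fisher's exact tests, as specified in the SAP, will be used to compare the response rates of any 2 vaccine arms". The threshold there is a two-sided p of at most 0.05. On the choice between the two tests, it says: "In general Barnard's is preferred since under most circumstances it is more powerful than Fisher's".

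The planning sizes come from Section 6.1, where the calculations "account for 10% of enrolled participants having missing data for the primary immunogenicity endpoint". Hence 15 × 0.9 = 13.5 and 5 × 0.9 = 4.5 are rounded down to 13 and 4. The supplied text contains no separate SAP section that settles the test, and no statistic for Barnard's test is given anywhere.

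**The concern.** The response-rate comparison between doses belongs to primary objective 2, and it is the only between-dose response-rate test that 6.1.2 singles out. Section 6.1.2 names one test for the analysis and describes its sensitivity with another. The analysis section permits both.

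With arms this small, exact tests are coarse, and two valid ones can give different decisions on the same data. Section 6.4.5.2 also lets a primary immunogenicity endpoint be analysed unblinded once its own visit is complete for everyone and at least 80% have data. Month 6.5 results could therefore be seen by arm before month 12.5 is analysed, so the test should be fixed before then. At stake are whether a borderline result is called significant, and whether the stated detectable differences describe the test that will be run.

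**Working it through.** **Inputs.** Arms of 13 (Group 2) and 4 (Group 1), two-sided alpha 0.05, from 6.1.2 and 6.4.4.1; enrolled sizes 15 and 5 from Table 3-1. The true-rate pairs used for power are my assumptions, with ranges shown.

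**1. Reproducing Table 6-5.** The arcsine normal approximation to Fisher's test with continuity correction is

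power = Φ{ 2[asin√(p₂ − 1/(2n₂)) − asin√(p₁ + 1/(2n₁))] / √(1/n₁ + 1/n₂) − 1.96 }.

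With n₁ = 4, n₂ = 13, p₁ = 0: p₂ = 0.88 gives 79.9% and p₂ = 0.89 gives 81.2%, so the first cell is 89, as printed. All 12 cells match this way. They do not match with n₁ = 13, n₂ = 4, the order in the caption, so the arm labels appear reversed.

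**2. The two tests at 13 vs 4.** There are 14 × 5 = 70 possible tables. Pooled Barnard uses z = (x₁/13 − x₂/4) / √[p(1−p)(1/13 + 1/4)], with p = (x₁ + x₂)/17. Its p-value is the probability of a |z| at least as large, maximised over the common rate.

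Worked case, 8/13 vs 0/4:
- Fisher: [C(13,8) + C(13,4)] / C(17,8) = (1287 + 715)/24310 = 0.082.
- Barnard: p = 8/17, z = 0.615/0.285 = 2.16, maximised p-value 0.042.

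Fisher for 11/13 vs 1/4: (312 + 13)/6188 = 0.053.

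| Group 2 vs Group 1 | Mirror table | Fisher p | Pooled Barnard p |
|---|---|---|---|
| 8/13 vs 0/4 | 5/13 vs 4/4 | 0.082 | 0.042 |
| 11/13 vs 1/4 | 2/13 vs 3/4 | 0.053 | 0.024 |

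These four are the only disagreements at 0.05.

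**3. Power and size at 13 vs 4** (rejection regions weighted by binomial probabilities).

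| True rates, n = 13 arm vs n = 4 arm | Fisher | Pooled Barnard | Gain (points) |
|---|---|---|---|
| 90% vs 30% | 56.2% | 66.4% | 10.2 |
| 80% vs 20% | 47.3% | 61.1% | 13.8 |
| 70% vs 10% | 44.8% | 60.7% | 15.9 |
| 62% vs 0% (largest over all rates) | 41.0% | 63.3% | 22.3 |

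Maximum size over a common rate: Fisher 1.8%, pooled Barnard 4.2%.

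**4. Nothing missing, 15 vs 5.** Of 16 × 6 = 96 tables, two change: 0/15 vs 2/5 and its mirror 15/15 vs 3/5 (Fisher 0.053, Barnard 0.021). Maximum size is 2.5% for both. Power, Fisher vs Barnard, is 67.8% vs 70.5% at 90% vs 30%, 62.1% vs 62.3% at 80% vs 20%, and 61.3% for both at 70% vs 10%. A large gap remains only near the boundary: 34.6 points at 0% in the n = 15 arm vs 40% in the n = 5 arm.

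**5. Detectable rates by enumeration, n = 4 arm at 0% to 5%, n = 13 arm higher.**

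| Basis | 80% power | 90% power |
|---|---|---|
| Table 6-5 as printed | 89–93% | 97–100% |
| Fisher, enumerated | 76–82% | 80–89% |
| Pooled Barnard, enumerated | 69–75% | 74–83% |

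In the first cell, 89 − 76 = 13 points come from the approximation and 76 − 69 = 7 from the choice of test. Direction matters too: with the n = 13 arm at 0%, pooled Barnard needs 59% (80% power) or 68% (90% power) in the n = 4 arm.

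**6. The statistic behind Barnard's name.** With an unpooled statistic at 13 vs 4, decisions differ from Fisher's in 8 of 70 tables, and in 6 of these Fisher rejects and Barnard does not. For 0/13 vs 2/4: Fisher 0.044, pooled 0.017, unpooled 0.18. For 11/13 vs 1/4: pooled 0.024, unpooled 0.118.

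**The case against.** The passages can largely be read together. Section 6.1.2 is specific to Group 1 vs Group 2, 6.4.4.1 is a general rule for every categorical endpoint, and both lean towards Barnard's. A separate SAP may settle the choice. The documents present the comparison as preliminary, concede limited power, and tie no decision to its p-value. All of this stands, and it keeps the point modest. It does not remove the either-or wording, the missing statistic, or detectable differences stated for a test that 6.1.2 does not plan.

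Three stronger readings are tempting and fail.

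- *The power statement is an error that invalidates the analysis.* Fisher's rejects in no table where pooled Barnard's does not, so powering on Fisher's is conservative.
- *The result generally turns on the test.* It does so in 4 of 70 tables at 13 vs 4. At the Table 6-5 pair of 0% vs 89%, with the n = 4 arm low, power is 99.0% vs 99.8%.
- *The tests differ as much at full enrolment.* A reader might cite 4/15 vs 4/5, for which a common software routine returns a Barnard p-value of 0.033, and a maximum size of 4.5% at 15 vs 5. Both come from mishandled ties in the statistic. The correct values are 0.0501 (Fisher 0.109, so neither rejects) and 2.5%.

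**Conclusion.** The mismatch is real and worth correcting, but it concerns stated figures and an unclosed choice and does not make the analysis invalid. At the protocol's planning sizes, using Fisher's in place of pooled Barnard's would forgo about 10 to 16 points of power at the three mid-range pairs, and up to about 22 points at the extreme, although Barnard's already holds the 5% level. At full enrolment the loss at those pairs is under 3 points.

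This rests on Barnard's test with the pooled score statistic, on evaluable arms of 13 and 4, and on assumed true rates. The 16-point figure is the largest gain on a grid from 10% to 90% in steps of 10 and is not an overall maximum. Whether the choice is still open in a separate SAP cannot be judged from the supplied text.

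**What to change.** 1. In 6.4.4.1, for the Group 1 vs Group 2 response-rate comparison, name Barnard's exact test, pooled score statistic, two-sided, alpha 0.05, matching 6.1.2. The statistic has to be written down because the unpooled version reverses some decisions.
2. In 6.1.2, restate the detectable differences by enumeration for that test and say which arm has n = 4, using the pooled Barnard row of step 5 for the case where that arm has the low rate.
3. In 6.1.2, replace the superiority wording, which could be read as one-sided, with a two-sided test of a difference, in line with 6.4.4.1.
4. Settle this before any unblinded month 6.5 analysis under 6.4.5.2.

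Cost: wording in two sections and one recalculated table. No added participants, visits or data.

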6.1.1 Sample size calculations for safety

The goal of the safety evaluation for this study is to identify safety concerns associated with product administration. The ability of the study to identify SAEs can be expressed by the true event rate above which at least 1 event would likely be observed and the true event rate below which no events would likely be observed. Specifically, in the Group 1 vaccine arm ($n = 5$), there is at least a 90% chance of observing at least one event, if the true rate is 37% or more, and there is at least a 90% chance of observing no events, if the true rate is 1% or less. In the Group 2 vaccine arm ($n = 15$), there is at least a 90% chance of observing at least 1 event if the true rate of such an event is 14.3% or more, and there is at least a 90% chance of observing no events if the true rate is 0.6% or less. In all vaccine arms of the study combined ($n = 20$), there is at least a 90% chance of observing at least one event, if the true rate is 10.9% or more, and there is at least a 90% chance of observing no events, if the true rate is 0.5% or less.

As a reference, in HVTN vaccine trials from April 2008 through March 2018 conducted in the US, about 1.7% of participants who received placebos experienced an SAE.

Binomial probabilities of observing 0, 1 or more, and 2 or more events among arms of size 15 and 5 are presented in Table 6-1 for a range of possible true adverse event rates. These calculations provide a more complete picture of the sensitivity of this study design to identify potential safety problems with the vaccine.

Table 6-1 Probability of observing 0 events, 1 or more events, and 2 or more events, among arms of size 15 and 5, for different true event rates

True event rate (%)	Pr(0/15)	Pr(1+/15)	Pr(2+/15)	Pr(0/5)	Pr(1+/5)	Pr(2+/5)
1	86	14	1	95.1	4.9	0.1
5	46.3	53.7	17.1	77.4	22.6	2.3
10	20.6	79.4	45.1	59	41	8.1
20	3.5	96.5	83.3	32.8	67.2	26.3
30	0.5	99.5	96.5	16.8	83.2	47.2
40	0	100	99.5	7.8	92.2	66.3

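### Above 20% missing data, Section 6.4.4.1 moves the dose comparison from an exact test to TMLE-type methods and claims valid inference without naming a reference distribution suited to about 4 versus 11 vaccinees

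*Combined protocol and SAP*

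**What the plan says.** Section 6.1.2 plans, for Group 1 versus Group 2, to "test superiority of the rate of responses targeting the 2F5 binding site" by Barnard's test. For response rates in general, Section 6.4.4.1 states that "exact tests, as specified in the SAP, will be used to compare the response rates of any 2 vaccine arms"; the tests meant are those of Barnard and Fisher, and the threshold is a two-sided p-value of at most 0.05. The vaccine arms are 5 and 15 (Section 6.1.1).

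Section 6.4.4.1 then splits by the amount of missing data. It expects some loss: "missing 10% of immunogenicity results for a specific assay is common". If no more than 20% of participants miss a value, complete-case methods apply. Above 20%, single-timepoint analyses go to methods of which TMLE is the named example. These are built on parametric generalized linear models (binomial for response rates, normal for quantitative endpoints), with covariate adjustment, weighting or imputation. The plan states: "These methods provide unbiased estimation and inferences under the parametric modeling assumptions", together with data missing at random. Repeated measurements go to linear mixed models. Secondary analyses of them "may be done using weighted generalized estimating equation (GEE) (37) methods, which are valid under MAR". The models must include every available baseline predictor of the missing outcomes.

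For this branch the documents give no standard error, reference distribution, small-sample correction or permutation test.

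**The concern.** Missing at random is an assumption about bias from missing values. It does not make a normal reference accurate when one arm has four people. An exact test keeps its level at any sample size. A Wald statistic with an influence-curve standard error relies on many participants per arm. When all, or none, of the few observed Group 1 vaccinees respond, that arm contributes zero estimated variance, and a modest difference is called significant.

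So the plan gives up its small-sample protection in the situation where Group 1 is likely to be smallest, and describes the replacement as valid. At stake is the between-dose p-value for primary endpoint 2: a chance difference could be reported as a dose effect.

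**Working it through.** **Plan's own figure.** The documents state no type I error for this branch, so there is none to reproduce. Table 6-5 gives power for Fisher's test at 13 versus 4, which belongs to the complete-case branch. (Its entries did not reproduce from the stated inputs. That is a separate matter and is not used here.)

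**Inputs.** Vaccinees 5 and 15; two-sided 0.05; trigger above 20%; expected loss 10% (Sections 6.1 and 6.4.4.1). Assumed, because the documents are silent: influence-curve standard error, normal reference, a common true response rate p in both arms, and 0, 1 or 2 covariates.

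**Observed arm sizes.** 20% of 20 vaccinees is 4 and 20% of 24 participants is 4.8, so the trigger needs at least 5 missing on either count. If all 5 are vaccinees, 15 remain, split for example 5/10, 4/11 or 3/12.

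**One data set, three tests.** Take 4/4 versus 8/11 responders. Without covariates, TMLE with an influence-curve standard error reduces to the unpooled Wald test:
- difference = 1 − 0.727 = 0.273
- SE = √(0 + 0.727 × 0.273 / 11) = 0.134
- z = 2.03, p = 0.042

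Barnard gives 0.34 and Fisher 0.52 on the same data.

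**Exact null rejection rate.** Sum Bin(a; n₁, p) × Bin(b; n₂, p) over every outcome (a, b) with |z| ≥ 1.96, counting 0% versus 100% as a rejection. At 4 versus 11 and p = 0.7, the outcomes with 4/4 in Group 1 and at most 8/11 in Group 2 alone contribute 0.7⁴ × (1 − 0.313) = 0.240 × 0.687 = 0.165, out of a total of 0.202. The rates are symmetric in p and 1 − p:

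| Observed split | p = 50% | 30 or 70% | 20 or 80% | 10 or 90% | 5 or 95% | Maximum |
|---|---|---|---|---|---|---|
| 5 vs 15 (no loss) | 11.1% | 15.9% | 14.2% | 4.0% | 0.5% | 16.3% |
| 5 vs 10 | 12.0% | 14.8% | 13.1% | 4.8% | 1.0% | 15.0% |
| 4 vs 11 | 13.8% | 20.2% | 18.7% | 7.7% | 2.1% | 20.7% |
| 4 vs 12 | 15.9% | 22.9% | 21.3% | 9.0% | 2.4% | 23.5% |
| 3 vs 12 | 24.8% | 29.9% | 26.1% | 10.0% | 2.3% | 30.0% |

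Barnard stays at about 5% or less, and Fisher at no more than 2.5%, at 5 vs 15 and 4 vs 11.

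**Simulated TMLE.** Starting from 5 vs 15 with at least 5 of 20 vaccinees missing and true rates of 10% to 90%, type I error was 4–23% with no covariate, 12–25% with one and 22–33% with two. A second set-up used one covariate and 25% average loss at random, keeping only trials above the trigger. It gave 21.8%, 22.3%, 22.9%, 18.3% and 8.3% at true rates of 30, 50, 70, 80 and 90%; Barnard on the same data gave 3.2%, 3.3%, 3.0%, 2.9% and 1.3%. A further one-covariate run gave 23–27% at 30–70%.

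**Other choices the text leaves open.** Logistic Wald: at most 1.7%. Score: at most 5.2%. Likelihood ratio: up to 8.6% at 5 vs 15 and 10.7% at 4 vs 11. For a quantitative endpoint, a normal-error model gives 4.8–5.3% with a t reference and 6.3–8.2% with z; a sandwich z gives 10.6–20.7%.

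**Chance of reaching the trigger.**
- One visit, 10% loss: P(Bin(20, 0.1) ≥ 5) = 4.3%; P(Bin(24, 0.1) ≥ 5) = 8.5%.
- Both primary visits counted together with independent losses, 1 − 0.9² = 19%: 33% and 49%.

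**The case against.** A reader might infer that a true null would be declared significant about 20% of the time. The documents do not support that as a fixed figure. TMLE is given only as an example, no influence-curve z test is named, and a binomial model with a logistic Wald test, which is conservative, is equally open. With all 5 and 15 vaccinees observed, the unadjusted test peaks at 16.3%; reaching 20% needs the reduced arms or a covariate.

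A reader might also infer that weighted GEE replaces the exact test. It does not: it is an optional secondary analysis of repeated measurements.

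Three further objections have force. First, the excess fades at extreme response rates. In the macaque studies (Section 4.7.1.4), all animals in both alum-containing arms had MPER-specific antibodies after two doses; if human rates were near 95%, the unadjusted test would reject 2.1% of the time at 4 vs 11. Second, the 49% trigger chance requires pooling two visits with independent losses, whereas Section 6.1 applies 10% to the primary endpoint and Section 6.4.4.1 speaks of a specific timepoint. Early termination would also make losses correlated. Averaged over both branches at one visit, 0.085 × 22% + 0.915 × (3.3% to 5%) gives only about 5% to 6%. Third, the stakes are limited: Section 6.1.2 describes its immunogenicity aim as preliminary estimation and concedes limited power, and no decision rule hangs on this p-value.

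These points limit the size and frequency of the problem. They do not supply the missing reference distribution. The averaged rate is no defence either, because the reported p-value would come from whichever branch was entered. Section 6.1.2 names Barnard's test with no exception for missing data, which leaves unclear which result governs above 20%.

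**Conclusion.** The concern holds in a bounded form. Above 20% missing, the plan claims valid inference that its named method, run in its usual form, does not deliver at this sample size. Under influence-curve TMLE with a normal reference, type I error is roughly 4–33%: an unadjusted peak of about 21% at 4 vs 11, about 20–27% with one covariate at true rates of 30–70%, and unadjusted values falling towards or below 5% at very high or low rates. The requirement to include all available baseline predictors pushes towards the upper part of that range.

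These figures assume the standard error and reference stated above, equal true rates in the two arms, and about 15 observed vaccinees. Permitted alternatives run from under 2% to about 11%, so the error rate is undetermined by the plan rather than known to be 20%. The branch is reached about 4–9% of the time at 10% loss at one visit, and 33–49% only if two independent visits are counted together. Separate SAP text might settle the choice, but none is in the documents. The point deserves a change because it concerns primary endpoint 2 and is nearly free to correct.

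**What to change.** In Section 6.4.4.1, or the SAP text that implements it:

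- Above 20% missing, keep the adjusted estimate but do not take the between-arm p-value from a large-sample normal reference. Permute vaccine-arm labels across participants, each carrying their covariates and missingness pattern (and weights, if used), and apply this to the adjusted difference. There are C(20, 5) = 15,504 allocations, so full enumeration is possible.
- State what this assumes: under the null, missingness does not depend on dose arm, and the two groups are exchangeable although dose escalation enrols them one after the other. It is not exact otherwise.
- Always report Barnard's test on observed data beside it, noting that it too needs ignorable missingness. Alternatively, label the adjusted comparison descriptive.
- Limit the claims of unbiased inference and of validity under missing at random to large samples.
- If the optional weighted GEE is run, use a small-sample-corrected sandwich with a t reference.

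In simulation, the permutation of a weighted rate difference rejected 3.6–5.2% of true nulls at rates of 30–90%, against 5.8–24.0% for its Wald version. The cost is wording, a few lines of code and somewhat fewer rejections. The corrected sandwich with t on Group 1 degrees of freedom is conservative (1.2–1.6% for a two-visit Gaussian outcome with assumed within-person correlation 0.6). No new data are needed.
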